30.2 Appendix B- RECIST

Modified-Response Evaluation Criteria in Solid Tumors (RECIST1.1) Quick Reference:

Eligibility

Only patients with measurable disease at baseline should be included in protocols where objective tumor response is the primary endpoint.

Measurable disease - the presence of at least one measurable lesion. If the measurable disease is restricted to a solitary lesion, its neoplastic nature should be confirmed by histology.

Measurable lesions - lesions that can be accurately measured in at least one dimension with longest diameter ≥ 5 mm using conventional techniques.

Non-measurable lesions - all small lesions (longest diameter < 5 mm with conventional techniques)

Methods of Measurement –

- All measurements should be taken and recorded in metric notation, using a ruler or calipers. All baseline evaluations should be performed as closely as possible to the beginning of treatment and never more than 4 weeks before the beginning of the treatment.
- The same method of assessment and the same technique should be used to characterize each identified and reported lesion at baseline and during follow-up.
- Clinical lesions will only be considered measurable when they are superficial (e.g., skin nodules). For the case of skin lesions, documentation by color photography, including a ruler to estimate the size of the lesion, is recommended.
- Histology can be used to differentiate between PR and CR in rare cases (e.g., after treatment to differentiate between residual benign lesions (e.g. scar) and residual malignant lesions).
- When the primary endpoint of the study is objective response evaluation, ultrasound (US) should not be used to measure tumor lesions. It is, however, a possible alternative to clinical measurements of superficial palpable lymph nodes, subcutaneous lesions and thyroid nodules. US might also be useful to confirm the complete disappearance of superficial lesions usually assessed by clinical examination.

Baseline documentation of Target Lesions

- All measurable lesions up to a maximum of five TILs and ten TNILs per subject should be identified as *target lesions* and recorded and measured at baseline.
- Target lesions should be selected on the basis of their size (lesions with the longest diameter) and their suitability for accurate repeated measurements (either by imaging techniques or clinically).
- A sum of the longest diameter (LD) will be calculated and reported as the baseline sum LD for *both TILs and TNILs respectively*. The baseline sum LD will be used as reference by which to characterize the objective tumor.

Response Criteria:

Complete Response (CR):	Disappearance of all TILs
Partial Response (PR):	At least a 30% decrease in the sum of the LD of TILs, taking as reference the baseline sum LD
Progressive Disease (PD):	 >20% increase of at least 5 mm in the sum of the longest diameters of the target lesions Or increase in tumor burden ≥ 20% relative to nadir (minimum recorded tumor burden) Or the appearance of one or more new lesions confirmed by an assessment 8 weeks after the end of the injections (Visit 6).
Stable Disease (SD):	A decrease in tumor size <30% or an increase in size <20% that is less than 5 mm in the sum of LDs of the TILs compared with the smallest sum of the LD recorded.

Evaluation of TILs

Evaluation of TNILs

Complete Response (CR):	Disappearance of all TNILs
Partial Response (PR):	At least a 30% decrease in the sum of the diameters of TNILs, taking as reference the baseline sum LD
Progressive Disease (PD):	 >20% increase of at least 5 mm in the sum of the longest diameters of the target lesions Or increase in tumor burden ≥ 20% relative to nadir (minimum recorded tumor burden) Or the appearance of one or more new lesions confirmed by an assessment at Visit 3.
Stable Disease (SD):	A decrease in tumor size <30% or an increase in size <20% that is less than 5 mm in the sum of LDs of the TNILs compared with the smallest sum of the LD recorded.

Evaluation of best overall response

The best overall response is the best response recorded from the start of the treatment until disease progression/recurrence (taking as reference for PD the smallest measurements recorded since the treatment started). In general, the patient's best response assignment will depend on the achievement of both measurement and confirmation criteria

TILs	TNILs	Recurrent TILs	Overall response
CR	CR	No	CR
CR	Incomplete response/SD/PD	No	CR
PR	Any	No	PR
SD	Any	No	SD
PD	Any	Yes or No	PD

Patients with a global deterioration of health status requiring discontinuation of treatment without objective evidence of disease progression at that time should be classified as having "symptomatic deterioration". Every effort should be made to document the objective progression even after discontinuation of treatment.

In some circumstances, it may be difficult to distinguish residual disease from normal tissue. When the evaluation of complete response depends on this determination, it is recommended that the residual lesion be investigated (fine needle aspirate/biopsy) to confirm the complete response status.

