9.4 Study Assessments

9.4.1 Tumor Measurements:

Tumor measurements will be done at each visit. Imaging assessment with high frequency ultrasound will be done at baseline and at the second follow-up visit (Visit 6). At baseline, up to 5 TILs that are at least 10cm apart will be selected to be followed over the course of the study. Up to 10 TNILs can be followed with no more than 2 TNILs selected in the same anatomical area as a TIL. Responses in TILs and TNILs will be measured serially. Clinical measurements will be performed with a millimeter measuring tape (Appendix A). All measurements will be selected that will be able to be followed clinically and for ultrasound evaluations. The RECIST 1.1 (Appendix B) response criteria will be used to evaluate tumor response. Individual tumor measurements will also be conducted to determine clinical management of TILs and TNILs. The timeframe for the clinical (primary endpoint) and evaluation will be at Visit 6 and for high-frequency ultrasound (secondary endpoints) at Visit 6 as well.

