9.4.1.1 Tumor Response

Complete Response (CR): Complete disappearance of all TILs (whether measurable or not, and no new lesions at the site of injection) confirmed by an assessment 8 weeks after the end of the injections (Visit 6).

Partial Response (PR): Decrease in tumor burden $\ge 30\%$ relative to baseline confirmed by an assessment 8 weeks after the end of the injections (Visit 6).

Duration of Overall Response (DOR): DOR is when the time measurement criteria are met for CR or PR (whichever status is recorded first) until the first date that recurrence or progressive disease (PD) is objectively documented, taking as reference for PD the smallest measurements recorded since the treatment started. If no recurrence or PD is documented after PR or CR is observed the time measurement will be performed at Visit 6 for PR and Visit 8 for CR.

Durable Response Rate (DRR): Measured from the time measurement criteria are met for CR or PR (whichever status is recorded first) with the response lasting continuously for > than or equal to 6 months. For PD, the reference will be the
smallest measurements recorded since the treatment started.

Time to progression (TTP): This will be measured from the time treatment is initiated until the first date that recurrence or progressive disease (PD) is objectively documented, taking as reference for PD the smallest measurements recorded since the treatment started.

Progressive Disease (PD): Progression is defined as >20% increase of at least 5 mm in the sum of the longest diameters of the target lesions or increase in tumor burden $\ge 20\%$ relative to nadir (minimum recorded tumor burden) or the appearance of one or more new lesions confirmed by an assessment 8 weeks after the end of the injections (Visit 6).

• **Rapid PD (RPD):** Is defined as an increase of >50% in tumor burden for lesions >2 cm in diameter or 100% tumor burden increase for lesion ≤2cm between visits.

Stable Disease (SD): Not meeting criteria for CR or PR, in absence of PD (Decrease of tumor size <30% to increase in size <20% of less than 5 mm in the sum of the longest diameters of the target lesions).

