16. STATISTICAL CONSIDERATIONS

16.1 Analysis Endpoints

16.1.1 Primary Endpoint

The primary end point is to evaluate the overall response rate (ORR) defined as proportion of subjects who achieved CR and PR in the cSCC TILs. Clinical assessments will be done using a ruler or calipers. Digital photograph of the lesion(s) will be recorded each visit. Through clinical evaluation, CR will be defined as the complete disappearance of all TILs and PR will be defined as at least a 30% decrease in the sum of the diameters of TILs, taking as reference the baseline sum diameters. Progression is defined as >20% increase of at least 5 mm in the sum of the longest diameter recorded or increase in tumor burden \ge 20% relative to nadir (minimum recorded tumor burden) or the appearance of recurrent lesions confirmed by an assessment 8 weeks after the end of the injections (Visit 6). Stable disease (SD) is defined as decrease in tumor size <30% or an increase in size <20%.

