16.1.2 Secondary Endpoints

 To assess the safety and adverse effect profile of talimogene laherparepvec in low risk cSCC. Adverse events to be assessed according to National Cancer Institute Common Terminology. This will be determined by incidence of all adverse events (AEs), grade ≥ 3 AEs, safety adverse events (SAEs), and events requiring the discontinuation of study drug, local effects on the tumor (ie, pain, inflammation and ulceration), and any clinically significant laboratory values.

- 2. Time to response in cSCC TILS. Time to response is the time from first visit until objective tumor response (CR or PR) is identified
- 3. Duration of overall response (DOR) of TILs. This will be measured from the time measurement criteria are met for CR or PR (whichever status is recorded first) until the first date that recurrence or progressive disease (PD) is objectively documented, taking as reference for PD the smallest measurements recorded since the treatment started. If no recurrence or PD is documented after PR or CR is observed the time measurement will be performed at Visit 8.
- 4. Durable response rate of TILs. The duration of overall response is ORR lasting continuously for > than or equal to 6 months.
- 5. Time to progression (TTP) of TILs. This will be measured from the time treatment is initiated until the first date that recurrence or progressive disease (PD) is objectively documented, taking as reference for PD the smallest measurements recorded since the treatment started.
- 6. Overall response rate (CR+PR) of TILs assessed by imaging technique (high frequency ultrasound) and correlate it with clinical overall response rate.
- 7. Overall clinical response rate (CR+PR) of individual TILs injected with talimogene laherparepvec (not as overall subject response). Overall response rate is defined as the proportion of injected lesions which achieved complete and partial response.

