16.2.1 Overall Response Rate (ORR)

The analysis of ORR will use a Simon two-stage optimum design to test that the proportion with ORR is \geq 80% (alternative hypothesis) versus ORR \leq 50% (null hypothesis). In the first stage, 7 patients will be recruited. If \leq 4 have ORR the trial will be terminated. If 5 or more have ORR, accrual will continue to the second stage. In the second stage, an additional 13 patients will be recruited. At the end of the second stage, if \geq 14 patients have ORR then TVEC will be considered promising for further study. This design yields 80% statistical power with a one-sided alpha level of 0.05.

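### The primary response has no single time rule: Visit 6 in 9.4.1 and 9.4.1.1, best response up to progression in Appendix B, and no visit in 16.1.1 or 16.3

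*Combined protocol and SAP*

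**What the plan says.** - **Section 9.4.1** fixes the time of the primary assessment: "The timeframe for the clinical (primary endpoint) and evaluation will be at Visit 6". It also adopts Appendix B as the criteria for tumor response.
- **Section 9.4.1.1** puts the same visit into the definitions. CR needs confirmation at Visit 6, and PR is a decrease of at least 30% "relative to baseline confirmed by an assessment 8 weeks after the end of the injections (Visit 6").
- **Appendix B** takes a different window: "The best overall response is the best response recorded from the start of the treatment until disease progression/recurrence". It adds that assignment depends on measurement and confirmation criteria. Its CR and PR rows for injected lesions name no visit, although its progression row names Visit 6.
- **Section 16.1.1** states that "PR will be defined as at least a 30% decrease in the sum of the diameters of TILs", measured against the baseline sum. It mentions Visit 6 only for progression.
- **Section 16.2.1** sets the Simon design: "In the first stage, 7 patients will be recruited", 13 more follow if at least 5 respond, and 14 or more responders of 20 is a promising result. The rates are 50% (null) and 80% (alternative).
- **Section 16.3** has stage 1 responders counted on an ongoing basis, with notice to the investigators when five have responded. It names no visit.
- **Section 16.1.2, item 2** dates response from when it is first seen: "Time to response is the time from first visit until objective tumor response (CR or PR) is identified".

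**The concern.** The count of responders is the only input to both Simon decisions, and the text that defines the count for the test does not say when a response must be present. Two kinds of subject are classified differently by the Visit 6 rule and by best response without confirmation:

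1. PR at an earlier visit, stable disease at Visit 6. Table 7 in Section 9.4.1.2 foresees this at lesion level.
2. Stable disease at Visit 6, first CR or PR at Visit 7 or 8. Table 7 offers alternative therapy to lesions without a response by Visit 6. The Appendix B window closes only at progression or recurrence and does not exclude assessments after other treatment. Read literally, it could credit the study drug with the effect of another therapy.

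With 20 subjects in one arm, a single reclassification moves 13 responders to 14, or 4 of 7 to 5 of 7. Leaving the rule open also allows it to be settled after the data are seen. Time to response and duration of response run from the first recorded response, so they could include subjects who are non-responders in the Visit 6 ORR.

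**Working it through.** **1. Reproduce the design (Section 16.2.1).** Inputs: n1 = 7, continue at 5 or more; 13 further subjects; success at 14 or more of 20; p0 = 0.50, p1 = 0.80; stated one-sided alpha 0.05 and power 80%.

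P(promising | p) = sum over x = 5, 6, 7 of C(7,x) p^x (1−p)^(7−x) × P(Y ≥ 14 − x), with Y ~ Binomial(13, p).

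- p = 0.50: 0.1641 × 0.1334 + 0.0547 × 0.2905 + 0.0078 × 0.5000 = 0.0219 + 0.0159 + 0.0039 = **0.0417**.
- p = 0.80: 0.2753 × 0.9009 + 0.3670 × 0.9700 + 0.2097 × 0.9930 = 0.2480 + 0.3560 + 0.2082 = **0.8122**.

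Both agree with the plan, reading 0.05 as a ceiling for a discrete test.

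**2. Classify example subjects under each reading.**

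| Course | Visit 6 rule (9.4.1, 9.4.1.1) | Appendix B with Visit 6 confirmation | Appendix B without confirmation |
|---|---|---|---|
| PR at Visit 5, PR at Visit 6 | responder | responder | responder |
| PR at Visit 5, SD at Visit 6 | not | not | responder |
| SD at Visit 6, first PR at Visit 7 or 8 | not | not | responder |

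The readings part only where confirmation is not applied. In that case the counted rate can only rise, except for a subject who met progression before Visit 6 and was then in response at Visit 6.

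A smaller ambiguity remains within 9.4.1.1. Confirmed at Visit 6 may mean the status at that visit, or an earlier response that persists to it. A response first seen at Visit 6 counts only under the former.

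**3. Conditional effect on type I error.** Assume that the 50% null refers to Visit 6 status, and that a share q of Visit 6 non-responders is counted under unconfirmed best response. The counted rate is then p = 0.50 + 0.50q.

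| q | counted rate | P(promising) |
|---|---|---|
| 0% | 0.50 | 0.042 |
| 2% | 0.51 | 0.0499 |
| 4% | 0.52 | 0.059 |
| 10% | 0.55 | 0.096 |
| 20% | 0.60 | 0.189 |

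The 0.05 level is crossed at a counted rate of about 0.510. The documents give no value for q.

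**The case against.** The best defence is that the sections, read together, already give one rule. Section 9.4.1 names Visit 6 for the primary endpoint. Section 9.4.1.1 requires confirmation of CR and PR at Visit 6. Appendix B makes best response depend on confirmation, and the only confirmation stated for CR or PR is the one in 9.4.1.1. Appendix B is labelled a quick reference, and no section names best overall response as the primary endpoint or as the Simon input. Table 7 also treats Visit 6 as the decision point: CR of an injected lesion is to be determined by then at the latest, and lesions without a response are offered other treatment, so late first responses should be few.

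Most of this stands, and it shows that Visit 6 is the likely intent. It does not close the gap. Appendix B does not refer to 9.4.1.1 for its confirmation criteria. Sections 16.1.1 and 16.3, from which the test is run, repeat neither the visit nor the confirmation. The offer of other treatment makes a late response harder to interpret but does not exclude it from the Appendix B window.

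Dating time to response and duration from first recording is also compatible with a responder group fixed at Visit 6. It only needs to be said.

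**Conclusion.** The time rule for the primary response is inconsistent and should be fixed before responders are counted. The practical size is one or a few subjects, which is enough to change either decision when the cut-offs are 5 of 7 and 14 of 20.

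Three stronger conclusions are tempting, and the documents do not support them:

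- **That different subjects will be counted.** This follows only if the Visit 6 confirmation in 9.4.1.1 is not carried into Appendix B.
- **That the stated 0.05 alpha fails.** Type I error depends on the null rate and the cut-offs. If 50% is the null for whichever endpoint is counted, alpha is 0.042 under either rule. It passes 0.05 only if 50% means Visit 6 status and unconfirmed best response lifts the counted rate above about 51%. Section 16.2.1 does not say which endpoint the rates describe, so 0.096 and 0.189 are illustrations, not estimates.
- **That ruler error alone would supply 5 to 10 points of extra responders.** The documents give neither a measurement error nor a distribution of true shrinkage. Eligible lesions run from above 0.5 cm to below 5 cm. A 1 mm error is 10% of a 10 mm lesion but about 3% of a 30 mm lesion (1/30), so no general figure follows.

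**What to change.** - **Sections 16.1.1 and 16.3:** state that ORR for the Simon test, including the stage 1 count, is the proportion of treated subjects in CR or PR at Visit 6 relative to the baseline sum. Responses present only before or only after Visit 6 do not count. The 50% and 80% rates refer to this endpoint.
- **Appendix B:** state that best overall response is a supportive summary and is not used in the Simon test.
- **Duration of response:** compute it in responders as defined in 16.1.1, dated from the first recording.
- **Time to response:** use the same responder definition, with non-responders censored as in 16.2.6.

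The cost is a few sentences. Sample size, cut-offs and visits do not change. The downside is that transient and late responders no longer count, so the reported ORR may be slightly lower. They remain visible in the supportive best-response summary.

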30.3 Appendix C- Safety Reporting Submission Forms

Sample Fax Cover Form for Individual Safety Reports (Amgen Global Safety)

Investiga Amgen ISS < <ls FAX</ls 	PS - enter Form Type>> * tor Sponsored Study SO/SOPS - Select Category>> Transmittal Form DPS - Enter Product>>
	mber>> / < <lso -="" enter="" id,="" if
. If none, delete line>></lso>
To: Amgen Global Safety, < <lso -="" enter="" location="" sops="">></lso>	AMGEN ISS PROTOCOL #:
Phone No: Phone No: < N/A for US>> Fax No: < Sax # same Fax # same Same Same Same www.example.com"/>www.example.com www.example.com www.example.com www.example.com www.example.com www.example.com"/>www.example.com www.example.com"/>www.example.com www.example.com	

Sample Fax Cover Form for Aggregate Safety Reporting

Investigat FA	gate Safety Reporting or Sponsored Study (ISS) X Transmittal Form ogene Laherparepvec, T-VEC)
To: NASCR Study Management Email : < <nascr manager="">></nascr>	AMGEN ISS PROTOCOL #:
Use this form as a cover page for all ag Fax transmission contents (Check a Description of Reports	
Adverse Events Summary Tag (all serious and non-serious e	events, regardless of relatedness)
US IND Annual Report, Date: Other Aggregate Analyses (p End of Study Final Report Other (please specify:	lease specify:)
Total # of pages in this transmissio	n, including cover page:

Sample of Report of Suspected IMLYGIC™ (Talimogene laherparepvec) or Herpes Virus Associated Adverse Event

Relationship: Patient Health Care Professional Observatic IMLYGIC (TVEC) ADMINISTRATION, if applicable (Please ind cate dates as £ DMI IV/YY) Is patient receiving IMLYGIC? IMLYGIC Explosure: IMsYGI first administered (date) Yes No (If no, skip this section) NulyGIC Dose Frequency Route If yes, please specificates and Paties and Patient IMLYGIC Batch # Exp Date Batch # unknown If yes, date of last dosed iscontinued in an antibody test for herpes simpler virus type-1 (figrefice there is the elagnosis ben confirmed will aboratory tests? (rives please provide results in table below) Previous history of herpes infections: Describe how exposure occurred: Swabbeu for herpes simpler virus type-1 (figrefice test) Previous history of herpes infections: Describe how exposure occurred: Swabbeu for herpes simpler virus type-1 (figrefice test) Cold sores/fever blister (eg, on face, mouth, lip or nose) Physical Contact Swabbeu for herpes simpler virus type-1 (figrefice test) Bister lesions in genital area Caregiver Other Virus Other Bister lesions in genital area Dressing charane Other Virus Other	or Herpes V	(Talimogene lah irus Associated) ing the protection of personal informat ther than the specific information requ	Adverse Ever	n this form may be transferred and a	processed outside of the country in which it is coll ress, telephone number and government issued in	ected. Do not provide information dentifier.
Gender: Male Female Weight: Ib kg Age at time of event:	PATIENT / CASE ADMIN	ISTRATIVE INFORMA	TION (Please indic	ate dates as DD/MM/YYY	Y)	
Age at time of event:		With		Event Reported Term	Date of This Rep	port
Is patient receiving IMLYGIC? IMLYGIC Exposure: IMsYGIC first edministered (date) \Period Yes No (If no, skip this section) IMLYGIC Dose Frequency Route If yes, please specificates and feation IMLYGIC Batch # Exp Date Batch # unknown If yes, please specificates and feation SIGNS AND SYMPTOMS (Check all that apply, provide dates of onset, resolution if available) Swabbed or herpes simplex virus type-1 (frand/or has the diagnosis been confirmed without tests? (rives, please provide results) Previous history of herpes infections: Describe how exposure occurred: Swabbed or herpes simplex virus type-1 (frand/or has the diagnosis been confirmed without tests? (rives, please provide results) Cold sores/fever bister (eg, on face, mouth, lip or nose) Physical Contact Swabbed for herpes simplex virus (if yes, please provide results) in table below) Cold sores/fever bister (eg, on face, mouth, lip or nose) Close Contact Steep together Other Bister lesions in central area Dressing channe Other Had an antibody test for herpes simplex virus (if yes, please provide results) in table below)	ge at time of event: elationship: 🔲 Patient	- Healt		·		Clinical Trial Observational study Post-marketing
☐ Yes ☐ No (If no, skip this section) Last IMLYGIC Base of MC/GIC were stronged in No. 4 Ye IMLYGIC Dose Frequency Route If yes, please specific dates and reason IMLYGIC Batch # Exp Date Batch # unknown If yes, please specific dates and reason SIGNS AND SYMPTOMS (Check all that apply, provide dates of onset, resolution if available) Study drug discontinued with the dagnosis b, en confirmed with a contact: Bescribe how exposure occurred: Swabbed for herpes simple virus type-1 (h and/or has the dagnosis b, en confirmed with a blow) Cold sores/fever blister (eg, on face, mouth, lip or nose) Colds contact Swabbed for herpes simplex virus (If yes, please provide results in table below) Bister lesions in central area Coregiver Other Had an antibody test for herpes simplex virus (If yes, please provide results in table below)	IMLYGIC (TVEC) ADMII	ISTRATION, if applic	able (Please indicat	e dates as L D/M NY TYY		
IMLYGIC Dose Frequency Route If yes, please specify datas and the sog Study drug discontinued to go Yes C Very Review of last dose discontinued to go Yes C Very Review of last dose discontinued to go Yes C Very Review of last dose discontinued to go Yes C Very Review of last dose discontinued to go Yes C Very Review of last dose discontinued to go Yes C Very Review of last dose discontinued to go Yes C Very Review of last dose discontinued to go Yes C Very Review of last dose discontinued to go Yes C Very Review of last dose discontinued to go Yes C Very Review of last dose discontinued to go Yes C Very Review of last dose discontinued to go Yes C Very Review of last dose discontinued to go Yes C Very Review of last dose discontinued to go Very Review of last dose discontinued to go Yes C Very Review of last dose discontinued to go Very Review of last dose discontinued tof dose discontinued to go Very Review of last		this section)		ILYGIC Exposure: IMLYC ast IMLYGIC dise before e	event, tate)	
IMLYGIC Batch #Exp Date Batch # unknown If yes, date of last dose/discontinuation: SIGNS AND SYMPTOMS (Check all that apply, provide dates of onset, resolution if available) Swabbed or herpes infections: Previous history of herpes infections: Describe how exposure occurred: Swabbed or herpes simpler virus type-1 (Fandor has the diagnosis ben contirmed we laboratory tests? (Fives, please provide results) Skin lesion/rash – please describe: Image: Dotter describe: Stored lesion in Other Cold sores/fever blister (eg, on face, mouth, lip or nose) Close Contact Step together in Other Bister lesions in genital area Describe nome in contract we laboratory tests? (Fives, please provide results) Ves in No in Don't know	MLYGIC Dose	FrequencyR	oute It	ves blease specific dates :	and reason	
Previous history of herpes infections: Describe how exposure occurred: Swabbed for herpes simpler virus type-1 (fractional distribution of the diagnosis bien confirmed with the diagnosis bien confirmed withet diagnosis bien confirmed with the diagnosi	MLYGIC Batch #	Exp Date 🗌	S Batch # unknown f	udy drug discontinued yes, date of last dosc/disc	No Pres O Unknown	`
Cold sores/fever blister (eg. on face, mouth, lip or nose) Herpetic whitlow (paintul, itchy blister lesion on fingertips of hand) Dister lesions in genital area	SIGNS AND SYMPTOMS	(Check all that apply, pro	vide dates of onset, r	esolution if available)	study.	
Cold sores/fever blister (eg, on face, mouth, lip or nose) Herpetic whitlow (paintul, itchy blister lesion on fingertips of hand) Dister lesions in genital area Dister lesions in genital area Dister lesions in genital area	Yes: Last episode (dd/mm/yyyy	ribe:	Physical Contact:		. below)	
Blister lesions in genital area Dressing change Other Very Deta of test (def/ment/out)	Herpetic whitlow (painful, itch)	ce, mouth, lip or nose)	Sleep together	Other		-
Herpes keratitis – eye signs and/or symptoms: redness, pain, photophobia (intolerance to light), Others Treated with antivirals (eg, acyclovir) for a l	Blister lesions in genital area			Other		

Sample of Pregnancy Notification Worksheet

Investigator-Name		rative Information¤	H	
2Contact Information¤ Investigator Name: → Site-#·				
Investigator-Name	1		valional. "rriospective" Reliospective) 🔤	
Phone ()			- Cito #	
Institution				
Address·				
4Amgen-Product-Exposure-# subject-ID#- Amgen-Product# DossSubjeat-Gender:				
Subject ID #: Doss #ibiting Gender: Frequencyn Male Subject DOB#: Subject DOB#: Start Daten //dd //y #				
x x x x x y	4.⊷Amgen·Produc	:t·Exposure·¤	~	
x x x x x y	Subject ID #			
Did-the-subject-withdraw-from-the-study?··□··Yes····□··No¤ 5·Pregnancy-Information¤ Pregnant-female's·LMP······mm·/·dd/·yyyy····□·Unknown¶ Estimated-date-of-delivery···mm·/·dd/·yyyy····□·Unknown···□··N/A¶ → If·N/A,·date-of-termination-(actual-or-planned)·mm·/·dd/·yyyy····¶	publect Dr.#	Doso Upinnte Gender:	emale Male Subject DOB#: mm	·dd/ yyyy
Did-the-subject-withdraw-from-the-study?··□··Yes····□··No¤ The structure 5Pregnancy-Information¤ Pregnant female's LMP·····mm/·dd/·yyyy····□·Unknown¶ Estimated date of delivery···mm/·dd/·yyyy····□·Unknown • If N/A, date of termination (actual or planned)·mm/·dd/·yyyy····□	Amgen-Prodi	uct# DoseSubinateGender: I i conception# Freq	emale	·dd/·yyyy ate¤
Did-the-subject-withdraw-from-the-study?··□··Yes····□··No¤ The structure 5Pregnancy-Information¤ Pregnant female's LMP·····mm/·dd/·yyyy····□·Unknown¶ Estimated date of delivery···mm/·dd/·yyyy····□·Unknown • If N/A, date of termination (actual or planned)·mm/·dd/·yyyy····□		Conceptions		
Did-the-subject-withdraw-from-the-study?··□··Yes····□··No¤ The structure 5Pregnancy-Information¤ Pregnant female's LMP·····mm/·dd/·yyyy····□·Unknown¶ Estimated date of delivery···mm/·dd/·yyyy····□·Unknown • If N/A, date of termination (actual or planned)·mm/·dd/·yyyy····□		Conceptions		_/уууу¤
Did-the-subject-withdraw-from-the-study?··□··Yes····□··No¤ The structure 5Pregnancy-Information¤ Pregnant female's LMP·····mm/·dd/·yyyy····□·Unknown¶ Estimated date of delivery···mm/·dd/·yyyy····□·Unknown • If N/A, date of termination (actual or planned)·mm/·dd/·yyyy····□	H.	ц ц		_/уууу¤
5Pregnancy-Information Pregnant-female's-LMP······mm/-dd/-yyyy····⊡·Unknown¶ Estimated-date-of-delivery···mm/-dd/-yyyy····⊡·Unknown···-⊡·N/A¶ → If-N/A,-date-of-termination-(actual-or-planned)-mm/-dd/-yyyy····¶	⊭ Was∙the⊦Amgen∙pr	roucefunding		_/уууу¤
Pregnant-female's-LMP······mm·/·dd/·yyyy····□·Unknown¶ Estimated-date-of-delivery····mm·/·dd/·yyyy····□·Unknown····□·N/A¶ → If-N/A,-date-of-termination-(actual-or-planned)·mm·/·dd/·yyyy····¶	⊭ Was-the-Amgen-pr → If-yes,-provide	roduct-(or-study-drug)-discontinued?-*		_/уууу¤
Estimated date of delivery …mm/ dd/ yyyy□ Unknown …□ N/A¶	× Was∙the-Amgen∘pr → If·yes,·provide Did∙the·subject·witl	roduct-(or-study-drug)-discontinued?-f -product-(or-study-drug)-stop-date:mm hdraw-from-the-study?YesNo		_/уууу¤
→ If·N/A, date of termination (actual or planned) mm/ dd/ yyyy	was-the-Amgen-pr → If-yes,-provide Did-the-subject-with 5Pregnancy-Info	roduct-(or-study-drug)-discontinued?-1 	x Use customized for /de_/yyyy_ ¶ for the study	_/уууу¤
	× Was-the-Amgen.pr → If-yes,·provide Did-the-subject-witt 5Pregnancy-Info Pregnant-female's-LMF	rourepunue	× Use customized for /de_/yyyyy ¶ for the strug ⊡.Unknown¶	_/уууу¤
Has the pregnant female already delivered?	× Was-the-Amgen.pr → If-yes,·provide Did-the-subject-witt 5Pregnancy-Info Pregnant-female's-LMF	rourepunue	x Use customized for γes∞	_/уууу¤
	Was-the-Amgen-pr → If-yes, provide Did-the-subject-with 5Pregnancy-Info Pregnant-female's-LMF Estimated-date-of-delive	rourepunue	x Use castomized for Yes⊷ [∞] ···No¶ ···Vided for the strid /dd_/yyyy ¶ for the strid 	_/yyyy¤
	the Amgen pr fryes, provide he subject with Instrucy-Info female's LMF d date of delive A, date of term regnant fema	rourepunue # # roduct-(or-study-drug)-discontinued?·f□··· hdraw-from-the-study?··□··Yes·····□··Noi prmations ?·····mm·/·dd/·yyyy ery···mm·/·dd/·yyyy initation-(actual-or-planned)-mm·/	x Use customized for /de_/yyyy_ ¶ for the study 	_/уууу¤

Sample of Lactation Notification Worksheet

notoconstudy number.		۹	
Study-Design: -Intervention			08
2Contact-Information	a		
		→ Site #·	
Phone ()	Fax·()	Email	
Institution			
Address			
3Subject Information	7		
		-/-dd Pasevy xx	
	000,000.000.000.000.000.000		
4Amgen.Product.Exp	osure∙¤	Ala	
	Dose-at-time-of-		
		quericy¤ Revite¤ ` 🗸 🎝 🚬 St	act-Date¤
Amgen·Product¤	breast-feeding#		
	breast-reeding=	Provid Stomic	
Amgen-Product¤	breast-feeding¤ но	provided for	RAN
ц	ргеазстеериндн	Provided for the	RM
ж Was-the-Amgen-product-(c	به به معنی محمد معنی محمد معنی محمد محمد محمد محمد محمد محمد محمد محم	quercy= Rouge customic Star Provided for the Star Yes	RAN
₩ Was-the-Amgen·product-(c → If-yes, provide-product	ргеазстеериндн	/dd/vyvyy¶	R Ny
